4.2 Rationale for dose/regimen and duration of treatment

The dose and different regimens for brolucizumab are based on the following considerations:

- Brolucizumab is well tolerated at a dose of 6 mg administered three times every four weeks during the loading phase based on the previous clinical phase 3 program in which 1088 subjects with nAMD received brolucizumab (RTH258-C001 - HAWK and RTH258-C002 - HARRIER). The nAMD study results regarding q12w/q8w maintenance dosing interval support stretching the interval between injections during the maintenance-phase to reduce the treatment burden (see [Section 1.1](#)).
- CRTH258AUS04 (MERLIN) is a two-year, multicenter, randomized, double masked, phase IIIa study evaluating brolucizumab 6 mg q4w versus aflibercept 2 mg q4w in patients with nAMD with persistent fluid. Review of the 52-week FIR led to an urgent safety communication based on an increased incidence of intraocular inflammation (IOI) and related adverse events including retinal vasculitis (RV), and retinal vascular occlusion (RO) in patients with q4w dosing with brolucizumab beyond the “loading phase”. IOI including RV, and RO were reported at a higher frequency in brolucizumab 6 mg q4w when compared to aflibercept 2 mg q4w (IOI: 9.3% vs. 4.5% of which RV: 0.8% vs. 0.0%, RO: 2.0% vs. 0.0%, respectively). Therefore, the protocol contains the note to discontinue subjects from study treatment who require treatment every 4 weeks.

- The route of administration is an intravitreal injection as for all anti-VEGF treatments currently approved for the treatment of nAMD.
- Study duration of 52 weeks allows for one initial injection followed by four complete 12-week intervals to evaluate effect of non-loading on long-term efficacy and safety.

4.3 Rationale for choice of control drugs (comparator/placebo) or combination drugs

Not applicable.

4.4 Purpose and timing of interim analyses/design adaptations

Not applicable. No formal interim analysis will be performed.

4.5 Risks and benefits

Ranibizumab and aflibercept (both approved inhibitors of VEGF-A) have consistently demonstrated efficacy in VEGF-driven retinal pathologies, including nAMD, with benefits outweighing the risks and are considered standard of care for treatment of nAMD patients.

In both phase 3 studies (HAWK and HARRIER) in nAMD, brolucizumab demonstrated non-inferiority to aflibercept in mean change in BCVA from baseline to week 48. These results were achieved while a majority of subjects on brolucizumab 6 mg – 56% in HAWK and 51% in HARRIER – were maintained on a q12w dosing interval following the loading phase through week 48, i.e. with a reduced treatment frequency compared to aflibercept. Brolucizumab safety was comparable to aflibercept, with the overall incidence of adverse events balanced across all treatment groups in both studies.

The lower probability of disease activity after the head-to-head comparison at week 16, the greater reduction in CSFT through week 48 and the lower proportion of patients with SRF and/or IRF at the majority of visits through week 48 for brolucizumab 6 mg versus aflibercept 2 mg in HAWK and HARRIER are anticipated to confer a longer duration of effect. This might translate into greater durability and longer injection intervals for brolucizumab 6 mg, with non-inferior efficacy. The potential superior anatomical results and a reduced treatment and monitoring visit frequency will provide benefit to subjects and caregivers/physicians. Further details of the known and potential risks and benefits associated with brolucizumab are presented in the Investigator's Brochure (IB).

Since until now only treatment-naive patients have been investigated with brolucizumab 6.0 mg treatment, this study will give insights on treatment response in pretreated patients. With the presumed longer lasting efficacy of brolucizumab the treatment burden also for pretreated patients might be reduced.

The risk to subjects in this trial may be minimized by compliance with the eligibility criteria and study procedures, as well as close clinical monitoring described in [Section 6.7.2](#), [Section 8.4.3](#) and [Section 10](#).

Women of child-bearing potential must be informed that taking the study treatment may involve unknown risks to the fetus if pregnancy were to occur during the study, and agree that in order

to participate in the study they must adhere to the contraception requirements outlined in the exclusion criteria. If there is any question that the subject will not reliably comply, they should not be entered or continue in the study.

Intravitreal injections, including those with brolucizumab, have been associated with endophthalmitis and retinal detachments. Acute intraocular pressure (IOP) increases have also been reported.

Intraocular inflammation, including retinal vasculitis and/or retinal vascular occlusion may occur following the first intravitreal injection with brolucizumab and at any time of treatment. These events were observed more frequently early on during treatment.

Patients with a medical history of intraocular inflammation and/or retinal vascular occlusion in the year prior to treatment with brolucizumab are at risk of developing retinal vasculitis and/or retinal vascular occlusion and should be closely monitored.

In patients developing intraocular inflammation (IOI), including retinal vasculitis and/or retinal vascular occlusion, treatment with brolucizumab in the FALCON study should be discontinued and the events should be promptly managed.

In addition, based on USM (CRTH258AUS04 FIR), the brolucizumab dosing interval should not be less than 8 weeks beyond the loading period.

Based on clinical studies, IOI related adverse events, including retinal vasculitis and retinal vascular occlusion, were reported more frequently in female patients treated with brolucizumab than male patients (e.g. 5.3% females vs. 3.2% males in HAWK and HARRIER). A higher incidence was also observed in Japanese patients.

Overall, brolucizumab was well tolerated in clinical studies with nAMD subjects when treatment interval is not less than every 8 weeks after the first 3 monthly initial doses (loading phase). The risk/benefit profile for brolucizumab remains positive.

5 Population

The study population will be male and female patients ≥ 50 years old diagnosed with active choroidal neovascularization (CNV) secondary to AMD, treated previously for this disease and able to comply with study or follow-up procedures.

If both eyes are eligible as per the inclusion and exclusion criteria described below, the eye with the worse visual acuity should be selected for study eye, unless the investigator deems it more appropriate to select the eye with better visual acuity, based on medical reasons or local ethical requirements.

5.1 Inclusion criteria

The investigator will assess the eligibility of the patient and the study eye at the screening visit and confirm eligibility prior to randomization. Before enrollment, morphological eligibility must be confirmed by the central reading center as part of the screening period. Subjects eligible for inclusion in this study must meet **all** of the following criteria:

1. Signed informed consent must be obtained prior to participation in the study.
2. Male or female patients, ≥ 50 years of age at screening.

Study eye:

3. Active choroidal neovascularization (CNV) secondary to AMD that affects the central subfield, including retinal angiomatic proliferation (RAP) with a CNV component, confirmed by presence of active leakage from CNV seen by fluorescein angiography and sequelae of CNV, e.g. pigment epithelial detachment (PED), subretinal or sub-retinal pigment epithelium (sub-RPE) hemorrhage, blocked fluorescence, macular edema (intraretinal fluid (IRF) and/or subretinal fluid (SRF) and/or sub-retinal pigment epithelium (sub-RPE) fluid that affects the central subfield, as seen by SD-OCT) at screening as confirmed by central reading center. If active CNV according to the above explained activity criteria is not detectable in screening image data (no IRF and no SRF), presence of residual and/or recurrent fluid (IRF and / or SRF) within the last 6 months before baseline visit is also considered eligible. In this case, historical images must be submitted for analysis by the central reading center.
4. Pretreatment with any anti-VEGF drug for a maximum of five years (60 months). Patients should have shown functional and/or anatomical treatment response to the pretreatment(s), prior to participating in this study.
5. The treatment initiation phase with the current anti-VEGF must have been completed for at least 6 months with continuous treatment in a $\geq q4w$ to $\leq q12w$ injection interval (± 2 -day window, i.e., 26 to 86 days inclusive) before the baseline visit. At least 4 weeks (minimum 26 days) must have passed between the last anti-VEGF pretreatment and baseline.
6. BCVA score must be ≤ 83 and ≥ 38 letters at 4 meters starting distance using Early Treatment Diabetic Retinopathy Study (ETDRS)-like visual acuity charts (approximately Snellen equivalent of 20/25 and 20/200), at both screening and baseline.

5.2 Exclusion criteria

Subjects meeting any of the following criteria are not eligible for inclusion in this study.

Ocular conditions:

1. Concomitant conditions or ocular disorders in the study eye at screening or baseline which could, in the opinion of the investigator, prevent response to study treatment or may confound interpretation of study results, compromise visual acuity or require planned medical or surgical intervention during the 52-week study period (e.g. structural damage of the fovea, vitreous hemorrhage, retinal vein occlusion, retinal detachment, macular hole, choroidal neovascularization unrelated to age-related macular degeneration, diabetic retinopathy (except mild non-proliferative) and diabetic macular edema).

2. Any active intraocular or periocular infection or active intraocular inflammation (e.g. infectious conjunctivitis, keratitis, scleritis, endophthalmitis, infectious blepharitis, uveitis) in study eye at screening or baseline.
3. Uncontrolled glaucoma in the study eye defined as intraocular pressure (IOP) > 25 mmHg on medication, or according to investigator's judgment, at screening or baseline.
4. Presence of amblyopia, amaurosis or ocular disorders in the fellow eye with BCVA $< 20/200$ at screening (except when due to conditions whose surgery may improve VA, e.g. cataract).
5. Atrophy or fibrosis involving the center of the fovea in the study eye as confirmed by central reading center.
6. The total area of fibrosis or subretinal blood affecting the foveal center point comprising $\geq 50\%$ of the lesion area as well as chronic cystic lesions in the study eye as confirmed by central reading center.
7. Structural damage within 0.5 disc diameter of the center of the macula in the study eye, e.g. vitreomacular traction, epiretinal membrane, scar, laser burn, at the time of screening that in the investigator's opinion could preclude visual function improvement with treatment.

Ocular treatments:

8. Treatment with any anti-VEGF drug for > 5 years in the study eye.
9. Pretreatment with brolucizumab at any time in the study eye.
10. Previous treatment with investigational drugs in the last 6 months in the study eye.
11. Previous use of intraocular or periocular steroids (non-topical) in study eye.
12. Macular laser photocoagulation (focal/grid) or photodynamic therapy in the study eye at any time prior to baseline and peripheral laser photocoagulation in the study eye within 3 months prior to baseline.
13. Intraocular surgery in the study eye within 3 months prior to baseline.
14. Vitreoretinal surgery in the study eye at any time prior to baseline.
15. Aphakia with the absence of posterior capsule in the study eye.

Systemic conditions or treatments:

16. Stroke or myocardial infarction during the 6-month period prior to baseline.
17. End stage renal disease requiring dialysis or renal transplant.
18. Uncontrolled blood pressure defined as a systolic value ≥ 160 mmHg or diastolic value ≥ 100 mmHg at screening or baseline. (In case there is an elevated blood pressure measurement, it should be repeated after 20 minutes. If the repeat measurement is elevated, then the patient is not eligible to be enrolled into the study).
19. Systemic anti-VEGF therapy during the 3-month period prior to baseline.

20. Systemic medications known to be toxic to the lens, retina or optic nerve (e.g. deferoxamine, chloroquine/hydroxychloroquine, tamoxifen, phenothiazines and ethambutol) used during the 6-month period prior to baseline except temporary use for Coronavirus SARS-CoV-2 (COVID-19) treatment.
21. History of hypersensitivity to any of the study drugs or their excipients or to drugs of similar classes, or clinically relevant sensitivity to fluorescein dye as assessed by the investigator.
22. History of malignancy of any organ system (other than localized basal cell carcinoma of the skin or *in situ* cervical cancer), treated or untreated, within the past 5 years, regardless of whether there is evidence of local recurrence or metastases.
23. History of a medical condition (e.g. metabolic dysfunction disease with exception of controlled type 1 or 2 diabetes mellitus, physical examination finding, or clinical laboratory finding) that, in the judgment of the investigator, would preclude scheduled study visits, completion of the study, or a safe administration of investigational product.

Other:

24. Patients on an investigational drug, biologic, or participated in a device study shorter than 5 half lives of the respective investigational drug, or < 30 days, or until the expected pharmacological effect has returned to baseline, whichever is longer.
25. Pregnant or nursing (lactating) women, where pregnancy is defined as the state of a female after conception and until the termination of gestation, confirmed by a positive human chorionic gonadotropin (hCG) pregnancy test.
26. Women of child-bearing potential, defined as all women physiologically capable of becoming pregnant, **unless** they are using highly effective methods of contraception during the study drug administration and for 3 months after stopping the investigational medication. Highly effective contraception methods include:
 - Total abstinence (when this is in line with the preferred and usual lifestyle of the subject). Periodic abstinence (e.g. calendar, ovulation, symptothermal, post-ovulation methods) and withdrawal are not acceptable methods of contraception
 - Female sterilization (have had surgical bilateral oophorectomy with or without hysterectomy), total hysterectomy, or tubal ligation at least six weeks before taking study treatment. In case of oophorectomy alone, only when the reproductive status of the woman has been confirmed by follow up hormone level assessment
 - Male sterilization (at least 6 months prior to screening). For female subjects on the study, the vasectomized male partner should be the sole partner for that subject
 - Use of oral (estrogen and progesterone), injected, or implanted hormonal methods of contraception or placement of an intrauterine device (IUD) or intrauterine system (IUS), or other forms of hormonal contraception that have comparable efficacy (failure rate <1%), for example, hormone vaginal ring or transdermal hormone contraception.

In case of use of oral contraception, women should have been stable on the same pill for a minimum of 3 months before taking study treatment.

Women are considered post-menopausal and not of child-bearing potential if they have had 12 months of natural (spontaneous) amenorrhea with an appropriate clinical profile (e.g. age appropriate history of vasomotor symptoms) or have had surgical bilateral oophorectomy (with or without hysterectomy), total hysterectomy, or tubal ligation at least six weeks ago. In the case of oophorectomy alone, only when the reproductive status of the woman has been confirmed by follow up hormone level assessment is she considered not of child-bearing potential.

If local regulations deviate from the contraception methods listed above to prevent pregnancy, local regulations apply and will be described in the informed consent form (ICF).

6 Treatment

6.1 Study treatment

6.1.1 Investigational and control drugs

Table 6-1 Investigational drug

Investigational Drug	Pharmaceutical Dosage Form	Route of Administration	Supply Type	Sponsor (global or local)
Brolucizumab / RTH258 120mg/ml	Solution for injection	Intravitreal use	pre-filled syringe	local

The investigational treatment used in this study is brolucizumab 6 mg/0.05 mL. Brolucizumab is formulated as a sterile solution aseptically filled in a sterile syringe for single use containing sufficient brolucizumab to deliver a 6 mg dose when administering a volume of 0.05 mL. The content of the study drug pre-filled syringe must **not** be split. Brolucizumab will be packed according to local legal requirements.

The storage conditions will be described on the package and follow the current recommendations of the manufacturer. Study medication should not be stored together with commercial brolucizumab to avoid mix up.

The sponsor will ensure sufficient supplies of brolucizumab for treatment use to allow for completion of the study.

6.1.2 Additional study treatments

No other treatment beyond investigational drug are included in this trial.

6.1.3 Treatment arms/group

Eligible subjects will be randomly assigned at Baseline to one of the following two treatment arms in a 1:1 ratio:

- Brolucizumab 6 mg “**loading arm**”: 3 x 4-weekly initial injections followed by an injection every 12 weeks (q12w maintenance)
- Brolucizumab 6 mg “**non-loading arm**”: one initial injection followed by an injection every 12 weeks (q12w maintenance)

6.1.4 Treatment duration

The planned duration of treatment is maximum 48 weeks and determined by the treatment arm and q12w/q8w maintenance, respectively. Discontinuation of study treatment for a subject occurs when study drug is stopped earlier than the protocol planned duration and can be initiated by either the subject or the investigator.

Study treatment will also be discontinued for patients who require injections more frequently than every 8 weeks after the loading phase (week 8, loading arm) or baseline (non-loading arm).

In patients developing intraocular inflammation, including retinal vasculitis and/or retinal vascular occlusion, treatment with brolucizumab in the FALCON study should be discontinued and the events should be promptly managed.

Subjects who prematurely discontinue study treatment for any reason except for withdrawal of consent should continue in the study and carry out the scheduled visits and assessments, at the discretion of the subject and investigator.

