6.2.3 Rescue medication

There will be no rescue medication for nAMD in the study eye.

In case of lack of efficacy with investigational drug for nAMD and if the investigator deems it is in the best interest of the patient to receive prohibited treatment ([Section 6.2.2](#)) in the study eye, the investigator should follow the instructions for study treatment discontinuation or study discontinuation provided in [Section 9](#).

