9.1 Discontinuation

The investigator should discontinue study treatment for a given subject and/or withdraw the subject from the study if, on balance, he/she believes that continuation would be detrimental to the subject's well-being.

A subject will be considered to have completed the study when the subject has completed the last visit planned in the protocol.

The investigator and/or referring physician will recommend the appropriate follow-up medical care, if needed, for all subjects who are prematurely withdrawn from the study.

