9.1.1 Discontinuation of study treatment

Discontinuation of study treatment for a subject occurs when study treatment is stopped earlier than the protocol planned duration and can be initiated by either the subject or the investigator.

The investigator must discontinue study treatment for a given patient if, he/she believes that continuation would negatively impact the subject's well-being.

Study treatment must be discontinued under the following circumstances:

- Subject decision
- Pregnancy (see [Section 8.4.2](#) and [Section 10.1.4](#))
- Use of prohibited treatment (see [Section 6.2.2](#))
- Any situation in which continuation with study treatment might result in a safety risk to the subject
- Unsatisfactory therapeutic effect, e.g. a subject requires injections more frequently than every 8 weeks after the loading phase (week 8, loading arm) or baseline (non-loading arm).
- Subjects develop intraocular inflammation, retinal vasculitis and/or retinal vascular occlusion

If discontinuation of study treatment occurs, the investigator should make a reasonable effort to understand the primary reason for the subject's premature discontinuation of study treatment and record this information on the appropriate eCRF page.

Subjects who prematurely discontinue study treatment for any reason, except for withdrawal of consent (refer to [Section 9.1.2](#)), should continue in the study with all the scheduled visits and assessments (except disease stability assessment, administration of study treatment, post-injection assessment and adherence to prohibited medication list) until EOS. These patients can be switched to standard of care anti-VEGF IVT as per investigator's discretion. Any IVT injection is contraindicated in subjects with active intraocular or periocular infections and in subjects with active intraocular inflammation; therefore, the investigators must verify that these conditions are not present in the study eye prior to every injection.

Subjects who decide not to participate in the study further should NOT be considered withdrawn from the study, UNLESS they withdraw their consent (see [Section 9.1.2](#)). **Where possible, subjects should return for the EOS visit assessments to be performed as scheduled in Table 8-1.**

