12.4.3 Handling of missing values/censoring/discontinuations

As a primary approach, retrieved data will be included, irrespective of intercurrent events such as prohibited medication or treatment interruption or discontinuation (treatment policy, difference in all randomized patients). Details will be specified in the respective SAP. For

statistical analyses of continuous parameters, missing data in case of lost to follow-up will be accounted for in a mixed model for repeated measures (MMRM) assuming data after loss to follow-up are missing at random (MAR), and assuming almost all data will be retrieved. Thus, every effort must be made to follow-up on patients after treatment discontinuation up to end of study.

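### Protocol 6.1.4 makes follow-up after stopping study treatment discretionary, while 9.1.1 and the treatment-policy analysis in 12.4 rely on it continuing

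*Protocol*

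**What the plan says.** **Follow-up after stopping study treatment**

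- Protocol 6.1.4: subjects who stop early, other than by withdrawing consent, "should continue in the study and carry out the scheduled visits and assessments, at the discretion of the subject and investigator".
- Protocol 9.1.1, for the same subjects: they "should continue in the study with all the scheduled visits and assessments" until end of study. The only exception is withdrawal of consent, and there is no discretion clause. A change of therapy does not require leaving the study: "These patients can be switched to standard of care anti-VEGF IVT as per investigator's discretion". One of the listed reasons for stopping is "Unsatisfactory therapeutic effect, e.g. a subject requires injections more frequently than every 8 weeks". For abbreviated contact after a stop, 9.1.1 gives a minimum data set that includes BCVA, collected in clinic or by telephone or email.
- Protocol 9.1: "The investigator should discontinue study treatment for a given subject and/or withdraw the subject from the study" if continuing is judged detrimental to the subject's well-being.
- Protocol 6.2.3, on lack of efficacy where a prohibited treatment is wanted: "the investigator should follow the instructions for study treatment discontinuation or study discontinuation provided in" Section 9.

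**What the analysis relies on**

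- Protocol 12.4.1 and SAP 2.5.1: a treatment-policy estimand for BCVA change to the mean of weeks 40 to 52.
- Protocol 12.4.3 and SAP 2.5.3: data retrieved after a stop are used, "assuming data after loss to follow-up are missing at random (MAR), and assuming almost all data will be retrieved". The same sections ask for every effort at follow-up to end of study.
- Protocol 12.4.4 and SAP 2.5.4: no sensitivity analysis.
- Protocol 6.4: subjects, site staff and assessors know the arm; only the reading center is blind.

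**The concern.** A site that reads 6.1.4 may agree with the subject to end visits when study treatment stops. A site that reads 9.1.1 carries on to week 52. The primary analysis needs the second behaviour: under treatment policy, the later BCVA of patients who stopped is part of the effect being estimated.

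The patients concerned are not a random subset. Poor effect is itself a reason for stopping, so those who stop include those doing badly. The two people given the discretion both know the arm. Nor can equal loss between arms be presumed. The rule on needing injections more often than every 8 weeks applies from baseline in the non-loading arm and from week 8 in the loading arm, so the period at risk of such a stop differs by design.

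If follow-up ended selectively, the model would estimate the missing weeks 40 to 52 from each patient's earlier visits and from patients still observed. The arm with more unobserved failures would look too good, and no planned analysis would show it.

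**Working it through.** **1. The texts side by side**

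| | 6.1.4 | 9.1.1 | 12.4.3 |
|---|---|---|---|
| Who | stops study treatment, consent not withdrawn | same | same |
| Default | visits continue | visits continue to end of study | every effort to follow up to end of study |
| Who may depart from it | subject and investigator, at discretion | only by withdrawal of consent | not stated; almost all data assumed retrieved |

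All three share the default. The conflict is the discretion clause, which stands in 6.1.4 alone.

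Section 6.2.3 sets no follow-up rule of its own. It points to Section 9, where both prohibited treatment and unsatisfactory effect are reasons to stop study treatment, after which visits continue. It mentions study discontinuation without saying when that route applies. This is loose wording and a secondary matter.

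**2. The plan's own precision figure**

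Inputs: SD 13 letters and 25 per arm (23 at the time of Amendment 2), from Protocol 12.8.1 and SAP 3.

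Half-width = 1.96 × SD × √(2/n)

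- n = 25: 1.96 × 13 × √(2/25) = 7.21 letters, as stated.
- n = 23: 1.96 × 13 × √(2/23) = 7.51 letters, as stated.

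Neither figure allows for missing data.

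**3. Possible bias, on assumed values**

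The documents give no rate of treatment failure or of loss after stopping. The only related figure is the 10% drop-out expected when 490 patients were planned (Protocol 3). Let a share f of one arm be unobserved at weeks 40 to 52, with a true mean change D letters below the observed mean m of that arm. The true arm mean is (1 − f)m + f(m − D) = m − fD. The arm therefore looks too favourable by fD if earlier visits do not predict the later deficit.

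With loss in one arm only:

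| f | D = 5 | D = 10 | D = 15 |
|---|---|---|---|
| 10% | 0.5 | 1.0 | 1.5 |
| 20% (5 of 25) | 1.0 | 2.0 | 3.0 |

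With loss in both arms and the same D, the bias in the difference is (f1 − f0) × D:

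- 20% against 10%: 0.5, 1.0 and 1.5 letters for D = 5, 10 and 15.
- Equal shares: 0.

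These are upper values. The model in SAP 5.4.1 uses visits 2 to 14 with an unstructured covariance, so it conditions on each patient's earlier BCVA. Any part of D already visible before follow-up ended is partly recovered.

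**4. Precision**

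A complete-case half-width with equal loss in both arms:

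- 10% loss (22.5 per arm): 1.96 × 13 × √(2/22.5) = 7.60 letters.
- 20% loss (20 per arm): 1.96 × 13 × √(2/20) = 8.06 letters.

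**The case against.** The best defence is that this is one stray clause. Sections 6.1.4 and 9.1.1 share the same default, and both say should rather than must. Section 9.1.1 lets patients who stop receive standard-of-care anti-VEGF in the study eye while they remain in the study, so there is little reason to remove them. It also says that subjects who decide not to take part further are not counted as withdrawn unless they withdraw consent. BCVA is in the minimum data set, and 12.4.3 presses for follow-up. The analysis is descriptive with no non-inferiority test, and even 3 letters is well inside 7.21.

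Most of this stands as mitigation. It does not remove the clause, and a confidence interval does not cover bias.

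The defence also rules out several stronger readings that a reader might infer:

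- *The investigator alone may end follow-up under 6.1.4.* The discretion is given to subject and investigator together.
- *Section 6.2.3 is a second, independent way out for treatment failures.* It defers to Section 9.
- *Following 9.1.1 secures every week 40 to 52 value.* It asks for the end-of-study visit where possible and allows abbreviated or telephone contact.
- *Missing weeks are simply filled in from patients still under follow-up.* The model also uses each patient's own earlier visits.

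**Conclusion.** The inconsistency is in the current text and bears on the primary analysis. Section 6.1.4 permits what 9.1.1 does not and what 12.4.3 assumes will hardly occur. In an open-label trial with a treatment-policy estimand, a missing-at-random assumption and no sensitivity analysis, that leaves room for loss of week 40 to 52 BCVA related to arm and outcome.

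The size is unknown. With 10–20% loss in one arm and a deficit of 5–15 letters, all assumed, the bias is at most about 0.5–3 letters before any recovery by the MMRM. It is about zero if loss and outcomes are equal between arms. It is smaller than the 7.21-letter half-width, though the upper end is not trivial against the 5 letters that Protocol 4.1 calls clinically relevant. The documents do not support a claim that selective loss has happened or that the estimate is biased; they support only that the wording allows it and that no planned analysis would detect it.

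**What to change.** - **6.1.4:** delete the discretion clause and refer to 9.1.1, so that stopping study treatment does not by itself end BCVA follow-up. Keep the two existing ways out: withdrawal of consent and the well-being withdrawal in 9.1. A rule that only the subject may end visits would contradict 9.1.
- **6.2.3 (secondary):** reconcile the mention of study discontinuation with 9.1 and 9.1.1, for data collection only. Treatment decisions are unchanged.
- **If visits are already complete:** this is possible, since Amendment 2 is dated November 2022, follow-up lasts 52 weeks and the SAP approvals are dated April 2024. In that case report how many week 40 to 52 BCVA values were retrieved after a stop, by arm and reason for stopping. Add a simple delta-adjusted sensitivity analysis that lowers the estimated values of unobserved patients by a range of letters, separately by arm.

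Cost: two wording changes and some extra visits for patients off study treatment, or one table and slight extra analysis work.
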